7.3. Order of Study Assessments

The preferred order of assessments for study visits is as follows:

- Safety assessments (ECG must be performed first, followed by vital signs, where required)
- Demographics, medical history and concomitant medication review
- Clinical assessments (PROs must be performed prior to any interventional assessments including lab draws)
- Clinical laboratory tests
- Labs for RCL
- Labs for PK and immunogenicity
- Labs for PD
- Labs for exploratory biomarkers
- Study drug administration
- Synovial biopsy and/or synovial fluid collection and ultrasound evaluation of joints

Unscheduled safety assessments should take priority over any scheduled clinical or PK assessments.

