6.11. Method of Treatment Assignment and Blinding

This is an open-label study; all subjects will be treated with SBT777101. After a subject has provided informed consent, they will be provided with a unique screening number.

The Investigator, study site personnel, the laboratories assigned to analyze PK, PD, and ADA samples and all subjects will know the treatment allocation during the study. The Sponsor and designees will also know the treatment and dose that each subject receives.

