7.2.4. Safety Assessments

7.2.4.1. Physical Examinations

A complete physical examination or a symptom directed physical examinations will be performed.

- A complete physical examination will include, at a minimum, assessments of the
 cardiovascular, respiratory, gastrointestinal, and neurological systems. A
 genitourinary or breast examination is not required unless clinically indicated, in the
 opinion of the Investigator assessing the subject. Height and weight will also be
 measured and recorded.
- A symptom directed physical examination will include those organs, body sites required to assess the symptoms and associated findings.

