7.2.7.2. Efficacy Assessments

ACR and DAS28 response rates will be used to evaluate efficacy responses. Joint count assessments should be performed by the same assessor throughout the study where possible.

The components of these efficacy instruments include evaluation of:

- Swollen and tender joint count (includes assessment of 28 and 66 swollen joints and/or 28 and 68 tender joints)
- Subject's assessment of arthritis pain (using a 100 mm visual analogue scale (VAS))
- Subject's global assessment of arthritis (using a 100 mm VAS)
- Physician's global assessment of arthritis (using a 100 mm VAS)
- Health Assessment Questionnaire-Disability Index (HAQ-DI) to assess subject's physical functioning.

Fatigue will also be measured using the Functional Assessment of Chronic Illness Therapy - Fatigue (FACIT-F) score.

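### The preferred visit order lists patient-reported outcomes after the safety assessments and medication review, and protects them only from interventional procedures

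*Protocol*

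**What the plan says.** Section 7.3 introduces its list with "The preferred order of assessments for study visits is as follows". The first three entries are:

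1. "Safety assessments (ECG must be performed first, followed by vital signs, where required").
2. "Demographics, medical history and concomitant medication review".
3. "Clinical assessments (PROs must be performed prior to any interventional assessments including lab draws").

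Laboratory sampling, study drug administration and synovial sampling follow. A closing sentence gives unscheduled safety assessments priority over scheduled clinical or PK assessments.

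The content of the first entry is set elsewhere. Under the Safety Assessments heading, Section 7.2.4.1 states: "A complete physical examination or a symptom directed physical examinations will be performed". Section 8.2 counts the monitoring and recording of adverse events among the safety assessments, and Section 8.2.3 makes verbal questioning the preferred way to ask about them.

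The content of the third entry comes from Section 7.2.7, Clinical Assessments: the synovitis assessment, joint counts, physician global VAS and subject-reported items. Section 7.2.7.2 names among the components of the efficacy instruments "Subject's assessment of arthritis pain (using a 100 mm visual analogue scale (VAS"), "Subject's global assessment of arthritis (using a 100 mm VAS") and HAQ-DI. FACIT-F is measured in addition. ACR response rates and DAS28 are exploratory endpoints (Section 9.4.2.4).

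On blinding, Section 6.11 states: "This is an open-label study; all subjects will be treated with SBT777101". The investigator, site staff and subjects all know the allocation.

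**The concern.** The list already accepts that order can affect a patient-reported score, because it requires the PROs before lab draws and other interventional assessments. It gives no such protection against what precedes them in the list: questions about adverse events, a physical examination and a conversation about medication with staff who know the treatment. The third entry is also silent on sequence within itself, so a subject may score pain and global status after watching the joint count.

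What is at stake is how the subject-reported parts of ACR and DAS28 can be read. With no concurrent control, a shift in these scores caused by the preceding contact looks the same as a shift caused by treatment. Section 1.8 says the study is meant to inform dose selection for later studies, so the preliminary efficacy data will be used even though they are exploratory.

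**Working it through.** The plan states no figure on this point, so there is none to reproduce and no arithmetic applies. The check sets Section 7.3 against the schedules.

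**Step 1: which rules bind.** The order as a whole is preferred. Two items inside it are worded as requirements: ECG first, then vital signs, where required; and PROs before interventional assessments. No other section requires PROs before staff contact.

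**Step 2: what coincides with the PROs.** The visits below, from Appendices A and B, are those that carry the subject VAS (pain and global) and HAQ-DI. All of them also carry vital signs, concomitant-medication review, a joint count and the physician VAS.

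| Visit | ECG | Medical history | Adverse events | Physical exam | FACIT-F |
|---|---|---|---|---|---|
| Screening | yes | yes | limited* | full | no |
| Day -10 to -4 | no | yes | limited* | directed | yes |
| Week 2 | yes | no | all | directed | no |
| Week 4 | no | no | all | full | no |
| Week 8 | no | no | all | full | no |
| Week 12 | no | no | all | directed | no |
| Week 24 | no | no | all | directed | yes |
| Week 48 | yes | no | all | full | yes |
| Early termination | yes | no | all | full | yes |

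*Appendix A, footnote d restricts reporting before study drug to SAEs caused by a protocol-mandated intervention.

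**Step 3: what the table shows.**
- At all seven post-dose occasions, a site following the listed order records adverse events, examines the subject and reviews medication before the PROs.
- Medical history precedes the PROs only at the two pre-dose visits. Appendix B has no row for medical history or demographics.
- The ECG-first rule meets the post-dose PROs at three of the seven occasions: Week 2, Week 48 and early termination.
- The contact before the PROs is not the same before and after dosing. History is taken only before; full adverse-event recording applies only after. An influence on the scores therefore need not cancel in a change from baseline.

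**Step 4: order inside the third entry.** Section 7.2.7 groups the joint counts and physician VAS with the subject-reported items, and neither Section 7.2.7 nor Section 7.3 ranks them. Since the overall order is only preferred, the position of the PROs can also vary between sites and between visits.

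**The case against.** The strongest reply is that nothing here is wrong or contradictory. The order is only preferred, so a site that gives the questionnaires before the medication review complies. The protocol deliberately protects PROs from invasive procedures, and Section 8.2.3 asks for open-ended, non-leading questions. Adverse-event questioning is not named in the Section 7.3 list and enters it only through Section 8.2. The primary endpoint is safety, the efficacy endpoints are exploratory, FACIT-F is not a listed endpoint, and subjects know they received active drug whatever the order of the forms.

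Most of this stands and limits the point. It does not remove it: following the list as written still produces the sequence described, and making it optional leaves the sequence uncontrolled.

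Four stronger readings are tempting and are not supported:
- **That PROs are always scored after a staff interview covering medical history.** The order is not mandatory, and no medical history is scheduled after dosing.
- **That staff convey impressions of progress and so push scores towards improvement.** No section describes this, and the documents establish no direction.
- **That the effect can be stated in DAS28 units, or that PRO items alone could produce an ACR response.** Neither the DAS28 weights nor the ACR response rule is in the Protocol. Section 7.2.7.2 gives one joint list of components and no scoring.
- **That PROs should simply come first at every visit.** This would conflict with the requirement that the ECG be performed first.

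**Conclusion.** The point holds as a minor design improvement. The preferred order lists PROs after adverse-event recording, the physical examination and the medication review, leaves their place relative to the joint counts and physician VAS open, and protects them only from interventional procedures. In an open-label trial without a control, any resulting influence on subject pain, subject global and HAQ-DI cannot be told apart from a treatment effect in the exploratory ACR and DAS28 results.

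Its size is unknown: the documents give nothing from which to estimate it, and no figure should be attached. The conclusion rests on two readings. One is that safety assessments in Section 7.3 carry the content given in Sections 7.2.4 and 8.2. The other is that sites will generally follow a stated preferred order. The primary safety endpoint is not affected by this argument. Reordering would also leave untouched the expectation that comes from knowing the treatment; it removes only the part that could arise from contact earlier in the same visit.

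**What to change.** Reword the list in Section 7.3 as follows:

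1. ECG, then vital signs, where required.
2. Subject-completed pain VAS, global VAS, HAQ-DI and, where scheduled, FACIT-F.
3. Adverse-event questioning, history and medication review, and physical examination.
4. Joint counts, physician VAS and the remaining clinical assessments.
5. Laboratory sampling and the later steps in their present order.

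State that step 2 precedes steps 3 and 4 at every visit with PROs, pre-dose visits included, so that baseline and follow-up scores are collected under the same conditions. Keep the ECG-first rule, the rule that PROs precede interventional assessments, and the priority for unscheduled safety assessments.

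The cost is a small change to visit flow at sites. No visit, staff member, procedure or subject is added.

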7.4. Subject Discontinuation / Withdrawal and Replacement

7.4.1. Subject Discontinuation/ Withdrawal from the Study

Subjects may discontinue the study for any of the following reasons:

- Subject withdraws consent
- The study is terminated
- May be withdrawn at any time at the discretion of the Investigator for safety, behavioral, or compliance reasons
- The subject requires medical treatment prohibited by the protocol
- Failure to generate a SBT777101 dose that meets the required quality control (QC) and release criteria as defined by the Sponsor

If a subject takes a prohibited medication or receives rescue therapy outside of permitted guidelines, they should remain in the study and continue to attend visits and complete study assessments as described in the SoA (Appendix B).

7.4.1.1. Data Collected for Subjects Withdrawn from the Study

If a subject chooses to withdraw from the study after enrollment but prior to study Day 1, SBT777101 will not be administered. All subjects that are dosed with SBT777101 and withdraw from the study will be encouraged to enroll in the long term follow-up study at the time of withdrawal.

The date and reason for study withdrawal, if available, must be recorded in the subject's eCRF. An Early Termination (ET) visit (see Appendix B) will be conducted unless consent to do so is withdrawn.

- If a subject withdraws from the study, he/she may request destruction of any samples taken and not tested to prevent future testing. The Investigator must document this in the site study records.
- Any data already generated from samples collected up to the point of withdrawal of consent will not be removed from the study database.

7.4.2. Lost to Follow-Up

A subject will be considered lost to follow-up if he/she repeatedly fails to return for scheduled visits and is unable to be contacted by the study site.

The following actions must be taken if a subject fails to return to the clinic for a required study visit:

- The site must attempt to contact the subject and reschedule the missed visit as soon as possible, counsel the subject on the importance of maintaining the assigned visit schedule and ascertain whether the subject wishes to and/or should continue in the study.
- Before a subject is deemed lost to follow-up, the Investigator or designee must make every effort to regain contact with the subject (where possible, [3] telephone calls, and if necessary, a certified letter to the subject's last known mailing address or local equivalent methods). These contact attempts should be documented in the subject's medical record.

• Should the subject continue to be unreachable, he/she will be considered to have withdrawn from the study.

7.4.3. Subject Replacement

Subjects in dose escalation cohorts who have been dosed with SBT777101 and withdraw for reasons other than toxicity or are lost to follow-up before completing the safety evaluation period (up to study Day 28) will be replaced.

Additionally, a replacement subject may be enrolled in the study at the discretion of the Sponsor if one or more enrolled subjects are not fully evaluable for purposes of complete safety, PK or PD determination. These replacement subjects may be enrolled while the cohort is still ongoing or concurrently with subsequent cohorts.

Subjects in backfill cohorts that withdraw from the study will not be replaced.

7.5. Early Discontinuation of the Study or Study Site

The Sponsor has the right to terminate this study at any time for any reason. Reasons for terminating the study or study site may include, but are not limited to:

- Incidence or severity of adverse events in this or other studies indicating a potential health hazard to subjects
- Unsatisfactory subject recruitment, e.g., excessively slow
- Poor protocol adherence
- Incomplete or inaccurate data recording
- Poor compliance with the protocol, the requirements of the Institutional Review Board (IRB)/Independent Ethics Committee (IEC) or local health authorities, the Sponsor's procedures, or the International Council for Conference Harmonisation Technical Requirements for Pharmaceuticals for Human Use (ICH) guidelines for Good Clinical Practice (GCP)

In any instance of early discontinuation of the study or study site, the Sponsor will notify, in writing, the Investigators, regulatory authorities and ethics committees, and will specify the reason(s) for termination.

8. ASSESSMENT OF SAFETY

8.1. Safety Plan

This is the first study in which SBT777101 will be administered to humans. As such, the actual risks are unknown. The anticipated potential and theoretical safety risks for subjects are detailed in the sections below. Please refer to the Investigator Brochure for SBT777101 for a complete summary of safety information.

Measures will be taken to ensure the safety of subjects participating in this study, including the use of stringent inclusion and exclusion criteria (see Section 4), and rigorous monitoring

assessments as detailed in Section 8.1.1. As described in Section 3.1.1, all subjects receiving SBT777101 in dose escalation cohorts will be dosed at least 14 days apart and monitored for onset of DLTs for at least 28 days prior to dose escalation. In addition, subjects in backfill cohorts will be dosed 14 days apart. Dosing of subsequent subjects within cohorts and dose escalation decisions will be made by a SMC in collaboration with the study Investigators (see Section 3.3).

All subjects will be monitored closely for toxicity. Administration of SBT777101 will be performed in a setting with available emergency medical facilities and staff who are trained to monitor for and respond to medical emergencies. Subjects will be closely monitored for acute safety events at the site under direct supervision of medical staff post administration of study drug. Safety monitoring should be performed as described below:

- Subjects should remain in a supine or semi-reclined position prior to and for the duration of the infusion. Vital signs must be measured approximately 15 minutes prior to infusion, and approximately every 15 minutes during the infusion.
- Subjects must remain at the study site/medical facility under medical supervision for at least 24 hours from the start of the Day 1 study drug infusion through completion of procedures at the Day 2 study visit.
- Subjects will be contacted by study staff on Days 3-7 to check for adverse events and provide reminders for temperature monitoring. Check-in may occur by phone call, text, or other method.
- The Sponsor recommends the following from study Day 2 to Day 28:
 - Subjects should stay within approximately 1 hour travel time to the study site from Day 2 through completion of procedures at the Day 7 study visit.
 - The subject remains under the care of a responsible adult in case of the onset of unexpected adverse medical events
 - The subject does not drive or operate heavy machinery

Subjects will be assessed clinically for adverse events during the conduct of this study using the CTCAE Grading Scale (Appendix E). All adverse events and serious adverse events will be recorded and reported as described in Section 8.2 and Appendix E.

8.1.1. Potential Risks

Risks potentially associated with SBT777101 treatment are described in the sections below. Please contact the Medical Monitor in case of questions on potential risks.

8.1.1.1. Infusion Related Reactions

Infusion related reactions are considered a potential risk for autologous cell therapies such as SBT777101. Pre-treatment with an antipyretic (e.g., acetaminophen 650 mg PO) and/or an antihistamine (e.g., diphenhydramine 25-50 mg PO or IV) is not required but may be administered as clinically indicated and at the discretion of the treating physician. Any infusion related adverse events will be reported in the eCRF and treatment given according to standard of care.

A blood sample for potential analyses of infusion reaction mediators (e.g., histamine, tryptase) should be collected at the time of an infusion related reaction AE.

The following guidelines should be followed for the management of infusion reactions:

- For mild reactions (Grade 1) with onset during an IV infusion, continue infusion of study drug at the same rate. Supportive care (e.g., antipyretics and/or antihistamines) may be administered as clinically indicated.
- For reactions of Grade 2 severity, pause SBT777101 infusion and administer supportive care. Study drug infusion may be re-initiated at a reduced rate (50%).
- For reactions of Grade 3 severity, pause SBT777101 infusion and administer supportive care. If symptoms resolve to ≤ Grade 2, study drug infusion may be re-initiated at a reduced rate (50%). If symptoms recur or worsen, discontinue infusion of study drug.
- For reactions of Grade 4, discontinue infusion of study drug.
- For reactions occurring after an IV infusion, apply supportive care as necessary.

Of note, SBT777101 is stable for 3 hours at room temperature; therefore, the time post-thawing should be monitored in the event that study drug infusion is paused, or the rate of administration is reduced.

8.1.1.2. Infections

Physicians should exercise caution when considering use of SBT777101 in subjects with a history of opportunistic and/or recurrent infections or those with underlying conditions that may predispose them to infections (e.g., diabetes). SBT777101 should not be administered to a subject with an active infection.

Close monitoring of subjects for signs of infection is recommended since they may be receiving concomitant therapy that could lessen the signs and symptoms of acute infections due to suppression of the acute phase response. Subjects should be instructed to monitor their temperature daily and to contact their physician immediately if experiencing symptoms that suggest infection in order to ensure rapid evaluation and appropriate treatment. All subjects with a fever (temperature >38°C or 100.4°F) should be evaluated for an infectious etiology.

See Section 7.1.2.4 for guidance on management of infections during the pre-treatment period of the study.

8.1.1.3. Viral Reactivation

While reactivation of viral (e.g., EBV) or other serious infections has been observed with biologic therapies for RA, the potential for this to occur with SBT777101 is unknown. Reactivation of latent viral infections is considered a potential risk for SBT777101 (Brunstein et al., 2013; Zhang et al., 2018). However, it should be noted that there has been no evidence of reactivation of viral or other serious infections observed in clinical trials in other autoimmune diseases using polyclonal T_{reg} adoptive immunotherapy. One subject in a Type 1 diabetes study developed grade 2 pharyngitis and had transient low-copy number cytomegalovirus (CMV), but

this was presumed to be due to a new infection with CMV occurring before receiving autologous polyclonal T_{reg} cells (Brunstein et al., 2011; Bluestone et al., 2015).

Subjects must be monitored closely for signs and symptoms suggesting potential reactivation of viruses and treated according to standard of care.

8.1.2. Theoretical Risks

Risks theoretically associated with SBT777101 treatment are described in the sections below.

8.1.2.1. Cytokine Release Syndrome

Cytokine Release Syndrome (CRS) is thought to result from a high level of immune activation of effector lymphocytes, macrophages and/or myeloid cells with subsequent massive release of proinflammatory cytokines. CRS is associated with markedly increased levels of IL-6, IL-10, TNF α and INF γ , and the sequelae may be severe or life-threatening. Administration of CAR Teff therapy is associated with CRS, with symptoms typically appearing within 14 days of CAR Teff administration (Chou and Turtle , 2020), with the overwhelming majority developing within 1-2 days.

Although the precise risk of CRS with SBT777101 is unknown, CRS was not observed in studies of polyclonal T_{regs} in patients with autoimmune indications (see SBT777101 Investigator Brochure). Therefore, it is important to closely monitor subjects for signs and symptoms of onset of CRS despite this low risk.

CRS may be associated with one or more of the following signs and symptoms:

- High fever (>39°C)
- Fatigue
- Nausea
- Headache
- Dyspnea
- Tachycardia
- Peripheral and/or pulmonary edema
- Coagulopathy

- Electrolyte abnormalities (e.g., hypophosphatemia, hypokalemia, hyponatremia)
- Rigors
- Fluid-refractory hypotension
- Respiratory failure/hypoxia
- Myalgia/arthralgia
- Anorexia
- Neurological abnormalities

The diagnosis of CRS requires a fever (temperature of $\geq 38^{\circ}$ C or 100.4°F). All subjects will be provided with infrared thermometers for at-home temperature evaluations and instructed to seek medical attention if they develop a temperature of $\geq 38^{\circ}$ C (100.4°F). It is critical to exclude potential infections during the initial evaluation of any subject presenting with a fever.

Laboratory studies for the evaluation of possible CRS should include markers of inflammation, especially IL-6 and IFN γ when available. Although C-reactive protein (CRP) is frequently elevated in CRS, it is often elevated in patients with RA in general. Therefore, a diagnosis of CRS should not rely solely on a finding of abnormal CRP.

Subjects should be treated according to site protocols for the management of CRS or standard clinical practice.

See Appendix F for guidance on grading CRS adverse events according to the ASTCT scale.

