5.2.1. Permitted Medications for RA

Details of the potential impact of permitted concomitant medications for RA with SBT777101 are provided in Appendix H.

The following medications are permitted during the study up to Week 48. Guidance on doses and routes of administration are provided below:

- NSAIDs (see Table 2 for guidance)
- Pain relief medications (see Table 2 for guidance)
- Oral corticosteroids (see Table 2 for guidance)
- csDMARDs (see Table 2 and Table 3 for guidance)

- o Methotrexate (≤25 mg SC, PO or IM QW)
- o Hydroxychloroquine (200 mg PO BID or 400 mg PO QD)
- bDMARDs (and biosimilar equivalents) (see Table 2 and Table 3 for guidance
 - o Adalimumab (40 mg SC QW or Q2W)
 - o Golimumab (50 mg SC once monthly)
 - o Infliximab (3-10 mg/kg IV Q4W Q8W)
 - o Certolizumab pegol (200 or 400 mg SC Q2W)
 - Etanercept (50 mg SC QW)
 - o Anakinra (100 mg SC QD)
 - o Tocilizumab (162 mg SC QW or Q2W; 4 or 8 mg/kg IV Q4W)
 - o Sarilumab (200 mg SC Q2W)

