	The dose must remain stable for at least 1 week before the synovial biopsy procedure and/or synovial fluid collection and the Week 12 study visit	
	If changes in dose are required, the increased dose must be no higher than 20 mg/day and must be tapered quickly, returning to the previous dose level within 2 weeks	
NSAIDs	NSAIDs (e.g., ibuprofen and naproxen) are permitted but should not be used in the 7 days prior to the post dose synovial tissue collection where possible.	
Pain relief medications	Short courses of pain relief medications (e.g., opioids and acetaminophen) are permitted.	

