7.2.4.3. Vital Signs

Vital sign assessments will be performed at specific timepoints during the study.

• Will include oral body temperature, systolic and diastolic blood pressure, and pulse and respiratory rate. Height and weight will be recorded at screening only.

- Blood pressure and heart rate measurements will be assessed after the subject has been rested for at least 5 minutes, in a quiet setting if possible, and in a supine or semi-reclined position.
- Oxygen saturation will be measured at screening, during apheresis and during infusion of study drug.

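### The CRS diagnosis and the CRS home prompt both rest on fever, yet drugs that can suppress fever are permitted at onset; a few sentences and five oximetry readings would close the gap

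*Protocol*

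**What the plan says.** **Diagnosis and prompt.** Protocol Section 8.1.2.1 says "The diagnosis of CRS requires a fever" of at least 38 °C and gives no exception. Subjects receive thermometers and are "instructed to seek medical attention if they develop a temperature of" 38 °C or more. That is the only instruction to subjects at home in the CRS section. On work-up it says "Laboratory studies for the evaluation of possible CRS should include markers of inflammation". On timing, it puts CRS onset after CAR Teff therapy typically within 14 days, "with the overwhelming majority developing within 1-2 days".

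**Grading.** Appendix F (ASTCT) has the temperature criterion in all four grades. Footnote a drops it for patients who have CRS and afterwards receive an antipyretic or an anticytokine drug, with tocilizumab and steroids as examples, and only for grading later severity.

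**Permitted drugs.** Section 5.2.1 allows background tocilizumab and sarilumab. Table 2 asks for stable DMARD doses after Day 1 and allows oral corticosteroids (background up to 10 mg/day, temporarily up to 20 mg/day) and NSAIDs. It adds: "Short courses of pain relief medications (e.g., opioids and acetaminophen) are permitted". Section 8.1.1.1 leaves "Pre-treatment with an antipyretic (e.g., acetaminophen 650 mg PO) and/or an antihistamine" to the treating physician.

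**Monitoring.** Section 7.2.4.3: "Oxygen saturation will be measured at screening, during apheresis and during infusion of study drug".

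**The concern.** Footnote a already accepts that antipyretics, tocilizumab and steroids make fever an unreliable criterion. It applies that reasoning only when the drug follows the diagnosis. In this population the order will often be reversed, because a subject who enters on tocilizumab or prednisone is expected to stay on it through the whole CRS window.

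Section 8.1.1.2 warns that concomitant therapy may blunt the signs of infection. The CRS section carries no such warning, although its required sign is fever.

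What is at stake is recognition and labelling. CRS is a named theoretical risk of a first-in-human CAR product, and the nature and severity of adverse events is part of the primary endpoint. A Grade 2-type episode without fever could be described as something else, and a subject at home could wait for a temperature that does not come.

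**Working it through.** The protocol gives no figure to reproduce, so the check applies its rules to one case: a subject on stable tocilizumab who, after discharge, develops otherwise unexplained hypotension not needing vasopressors, with a temperature below 38 °C.

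1. *Diagnosis (8.1.2.1).* Fever is required and absent, so the diagnosis is not met.
2. *Grade (Appendix F).* The temperature row is failed in all four grades.
3. *Waiver (Appendix F, footnote a).* It needs CRS first and the drug second. Here the drug came first, so it does not apply.
4. *Recording (Appendix E).* The diagnosis is to be recorded in preference to individual signs where possible. Without a diagnosis the event is entered as hypotension. The same reasoning gives hypoxia for an afebrile subject needing low-flow oxygen.
5. *Home prompt.* The CRS temperature trigger is not reached. What remains is the instruction in 8.1.1.2 to call for symptoms suggesting infection, staff contact on Days 3-7, and the recommendation in Section 8.1 that a responsible adult be present to Day 28.
6. *Detection at visits (Appendix B, 7.2.4.3).* Days 2, 4 or 5, 7, 11 and 14 have vital signs (including blood pressure, pulse and respiratory rate) and a physical examination. No oxygen saturation is specified after the infusion, although hypoxia is one of the two non-fever grading signs.
7. *Contact in the tail of the 14-day window.* Days 8-14 are 7 days, with visits on Days 11 and 14: 7 − 2 = 5 days without scheduled contact. By the protocol's own account most CAR Teff onsets come well before this.

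The same rules show what does not depend on the CRS label:

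- *DLT (3.3).* Any related treatment-emergent event of CTCAE Grade 3 or higher counts, apart from the exempted Grade 3 infusion reactions.
- *Work-up.* It is tied to possible CRS in 8.1.2.1 and to a suspected event in Appendix B footnote h, not to a confirmed fever.
- *Capture.* All adverse events after dosing are collected and graded. Exploratory inflammatory markers are drawn on Days 2, 7, 14, 21 and 28.

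A frequency would need the risk of CRS with this product and the share of episodes kept afebrile by a permitted drug. The protocol gives neither; it calls the precise risk unknown and also describes it as low.

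**The case against.** The strongest reply is that fever is part of the adopted consensus scale and that little turns on the label. Section 8.1.2.1 tells sites to monitor for signs and symptoms and lists dyspnea, tachycardia, rigors, hypotension and hypoxia among them. An investigator may test and treat on suspicion. A subject who needs oxygen, as Grade 2 hypoxia requires, is already under care. The period of highest risk falls largely within the supervised stay of at least 24 hours and the daily contacts that follow. Most of this stands, and it limits the point to a modest one.

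Three stronger readings are tempting and are not supported:

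- *That afebrile CRS could let a toxic dose be cleared.* The DLT rule does not use the CRS label, and no dosing rule refers to Grade 2 CRS. The halting rule for two or more similar related SAEs is worded on similarity of events; any effect of scattered terms on it would be indirect.
- *That work-up is barred without fever.* The triggers are possible and suspected CRS.
- *That a number of missed cases can be given.* Both inputs would be invented. Nor does the protocol show that low-dose prednisone or an NSAID would hold an episode below 38 °C; footnote a concerns drugs given after CRS has developed.

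What the reply does not meet is that these safeguards rely on an investigator suspecting CRS when the protocol says its diagnosis is not met, and on a subject at home seeking care for reasons the CRS instruction does not mention.

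**Conclusion.** The gap is real, of minor to moderate importance, and cheap to close. A subject already taking a fever-suppressing drug can have hypotension or hypoxia that fails the stated CRS diagnosis, falls outside the waiver, is recorded under component terms, and may prompt care later if it begins at home. Safety counting for escalation is intact.

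The conclusion rests on the protocol text and on one assumption, that these drugs can blunt fever at onset. Footnote a supports this in kind for antipyretics, tocilizumab and steroids. Sarilumab is included because Appendix H places it in the same IL-6 inhibitor class, and NSAIDs on general pharmacological grounds. How often it would happen cannot be stated.

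**What to change.** 1. In 8.1.2.1, for subjects taking an IL-6 receptor blocker, a corticosteroid, an antipyretic or an NSAID, state that absence of fever does not exclude suspected CRS. Otherwise unexplained hypotension or hypoxia in these subjects should trigger the existing Appendix B footnote h sample and be brought to the SMC's attention.
2. Leave the ASTCT grades in Appendix F unchanged. A separate adverse event category for such episodes is optional.
3. Extend the home instruction, for all subjects, to dyspnea, rigors or light-headedness as well as temperature.
4. Add oxygen saturation to the vital signs already scheduled on Days 2, 4 or 5, 7, 11 and 14.

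The cost is a few sentences, a line in the subject instructions and five bedside readings per subject, with no new visit and no new scheduled blood draw. The downside is that some events that are not CRS, including infusion reactions, will be worked up, since many subjects with RA may be on one of these drugs. Grade 1 CRS whose fever is fully suppressed cannot be recovered, because fever is its only criterion.
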